9.7.1 Sample Size

Table 2: Sample Size/Probability Estimates

Proportion re-treated in the nitazoxanide Group		Proportion Receiving Additional Treatment in the Placebo Group						
		0%	5%	10%	15%	20%	25%	30%
0%	91.3%	91.6%	91.7%	91.6%	91.8%	92.0%	92.3%	
5%	91.4%	91.5%	91.6%	91.2%	91.2%	91.8%	92.5%	
10%	-	91.5%	92.0%	91.2%	91.8%	91.2%	92.2%	
15%	-	-	90.7%	90.7%	91.0%	91.6%	91.8%	
20%	-	-	-	87.3%	87.1%	87.0%	87.7%	
25%	-	-	-	-	74.0%	73.9%	75.2%	
30%	-	-	-	-	-	-	40.0%	40.9%

10.2 Protocol Deviations

Table 3: Missing Diary Days by Treatment Group

Diary Days	Statistic (days/subject)	Nitazoxanide 500 mg (N = X)	Placebo (N = X)	All Subjects (N = X)
Imputed ^a	n	x	x	x
	Mean	xx.x	xx.x	xx.x
	Median	xx.x	xx.x	xx.x
	Standard Deviation	xx.x	xx.x	xx.x
	Minimum	x	x	x
	Maximum	x	x	x
Total Missing ^b	n	x	x	x
	Mean	xx.x	xx.x	xx.x
	Median	xx.x	xx.x	xx.x
	Standard Deviation	xx.x	xx.x	xx.x
	Minimum	x	x	x
	Maximum	x	x	x

N=Number of subjects enrolled.

n = Number of subjects with imputed/missing diary days.

^a Includes subjects with imputed diary days per imputation rules given in Section 9.7.2.2.

^b Includes subjects with any missing diary days

Table 4: Distribution of Protocol Deviations by Category, Type, and Treatment Group

Category	Deviation Type	Nitazoxanide 500 mg (N=X)		Placebo (N=X)		All Subjects (N=X)	
		No. of Subj.	No. of Dev.	No. of Subj.	No. of Dev.	No. of Subj.	No. of Dev.
Eligibility /enrollment	Any type						
	Did not meet inclusion criterion	x	x	x	x	x	x
	Met exclusion criterion						
	ICF not signed prior to study procedures						
	Other						
Treatment administration schedule	Any type						
	Out of window visit						
	Missed visit/visit not conducted						
	Missed treatment administration						
	Delayed treatment administration						
Follow-up visit schedule	Other						
	Any type						
	Out of window visit						
	Missed visit/visit not conducted						
Protocol procedure/assessment	Other						
	Any type						
	Incorrect version of ICF signed						
	Blood not collected						
	Urine not collected						
	Stool not collected						
	Other specimen not collected						
	Too few aliquots obtained						
	Specimen result not obtained						
	Required procedure not conducted						
	Required procedure done incorrectly						
Treatment administration	Study product temperature excursion						
	Specimen temperature excursion						
	Other						
	Any type						
Blinding policy/procedure	Required procedure done incorrectly						
	Study product temperature excursion						
	Other						
	Any type						
Treatment unblinded	Treatment unblinded						
	Other						

N=Number of subjects in the Safety Population

12.4.1 Individual Laboratory Measurements and Abnormal Laboratory Values

Table 5: Laboratory Adverse Event Grading Scale

Blood, Serum, or Plasma Chemistries ¹	Reference Range ²	LO/HI/N ³	Mild (Grade 1)	Moderate (Grade 2)	Severe (Grade 3)
Creatinine (mg/dL)		HI	>ULN - 1.5 x ULN	>1.5 – 3.0 x ULN	>3.0 x ULN
Blood Urea Nitrogen (BUN, mg/dL)		HI	>ULN - 26	27 - 31	>31
Alkaline phosphatase (U/L)		HI	>ULN – 2.5 x ULN	>2.5 – 5.0 x ULN	>5.0 x ULN
AST (U/L)		HI	>ULN – 3.0 x ULN	>3.0 – 5.0 x ULN	>5.0 x ULN
ALT (U/L)		HI	>ULN – 3.0 x ULN	>3.0 – 5.0 x ULN	>5.0 x ULN
Bilirubin, serum total (mg/dL)		HI	>ULN – 1.5 x ULN	>1.5 – 3.0 x ULN	>3.0 x ULN
Hematology	Reference Range ²	LO/HI/N ³	Mild (Grade 1)	Moderate (Grade 2)	Severe (Grade 3)
Hemoglobin (g/dL)		LO	<LLN – 10.0	<10.0 – 8.0	<8.0
White Blood Cell Count (WBC, K/CUMM)		HI	>ULN - 15.00	15.00 - 20.00	>20.00
		LO	<LLN – 3.0	<3.0 – 2.0	<2.0
Platelets (K/CUMM)		LO	<LLN - 75	<75 - 50	<50
Other Laboratory Parameters		LO/HI	Test result is associated with a mild sign or symptom.	Test result requires minimal, local or non-invasive intervention.	Test result requires an invasive medical or surgical intervention, or change in study dosing outside of the protocol defined dosing or discontinuation from the study treatment, or addition of new medication.

¹ Depending upon the lab used, references ranges, eligibility ranges and grading may be split out by sex and/or age.

² Reference range of individual study site laboratory

³ High, Low, Not Graded

ULN – upper limit of normal; LLN – lower limit of normal

14.1.1 Disposition of Subjects**Table 6: Subject Disposition by Treatment Group**

Subject Disposition	Nitazoxanide 500 mg (N=X)		Placebo (N=X)		All Subjects (N=X)	
	n	%	n	%	n	%
Enrolled/Randomized	x	100	x	100	x	100
Received Any Treatment	x	x.x	x	x.x	x	x.x
Received All Scheduled Treatments through Day 7 ^b	x	x.x	x	x.x	x	x.x
Received All Scheduled Treatments through Day 14 ^b						
Received All Scheduled Treatments through Day 21 ^b						
Received All Scheduled Treatments through Day 28 ^b						
Received any additional Nitazoxanide						
Received additional Nitazoxanide after Day 28						
Completed Study Day 60						
Completed Study Day 120						
Completed All Blood Draws ^c						
Completed All Stool Collections ^d						
Completed Follow-up (Study Day 180) ^b						
Terminated Early ^b						
Death						
Lost to Follow-Up						
Voluntary Withdrawal by Subject						
Withdrawal by Investigator						
Termination of Site/Study by Sponsor						
Other						

N = Number of subjects enrolled.

^a Subjects are included if they have data indicating the study treatment was distributed and at least one pill count completed.^b Refer to Section 16.2.1 for reasons subjects discontinued or terminated early.^c Blood draws for serum Ig assays.^d Stool or rectal swabs collected for virus detection and stool for Norovirus specific Ig assays.

Table 7: Analysis Populations by Treatment Group

[Implementation Note: The reasons listed here should match the SAP text that describes who will be excluded from analyses. Although subjects may meet multiple criteria for exclusion, they should be counted under only one reason for exclusion in this table. Priority for assigning reasons for exclusions will be defined in the SAP text.]

Analysis Populations	Reason Subjects Excluded	Nitazoxanide 500 mg (N=X)		Placebo (N=X)		All Subjects (N=X)	
		n	%	n	%	%	n
Modified Intention-to-Treat Population	Any Reason	x	xx	x	xx	x	xx
	Found to be ineligible at baseline						
	Did not receive at least one dose of study product						
Per Protocol Population	Any Reason						
	Found to be ineligible at baseline						
	Received less than 75% of scheduled doses through 28 days						
	Received additional Nitazoxanide 500 mg before primary outcome observed						
	Missed more than 1.5/7 days per week of the daily diary through 8 weeks (through Day 60)						
	Did not complete follow up						
Safety Population	Any Reason						
	Did not receive at least one dose of study product						
	Do not have a safety assessment						
Immunogenicity Population	Any Reason						
	Did not receive at least one dose of study product						
	Did not have at least one stool or serum immunoglobulin test result						

N=Number of subjects enrolled.

Note: Subjects who were excluded for more than one reason are only counted once. Reason excluded is prioritized as follows: ineligible at baseline, treatment compliance, additional Nitazoxanide 500 mg, diary compliance, and did not complete follow-up.

Table 8: Dates of First Treatment by Site and Treatment Group

[Implementation Note: Each site that enrolled subjects will have columns for Nitazoxanide 500 mg and placebo treatment groups.]

Site	Treatment Group	Date of First Dose						
		OCT2018-DEC2018	JAN2019-MAR2019	APR2019-JUN2019	JAN2021-MAR2021
Site 1	Nitazoxanide 500 mg (N = X)	x	x	x	x	x	x	x
	Placebo (N = X)							
	All Subjects (N = X)							
Site 2	Nitazoxanide 500 mg (N = X)							
	Placebo (N = X)							
	All Subjects (N = X)							
(Continue for All Sites that Enrolled Subjects)								

N = Number of subjects enrolled.

Table 9: Ineligibility Summary of Screen Failures

Inclusion/Exclusion Category	Inclusion/Exclusion Criterion	n ^a	% ^b
Inclusion and Exclusion	Number of subjects failing any eligibility criterion	x	100
Inclusion	Any inclusion criterion	x	xx
	[inclusion criterion 1]	x	xx
	[inclusion criterion 2]	x	xx
	[inclusion criterion 3]	x	xx
Exclusion	Any exclusion criterion	x	xx
	[exclusion criterion 1]	x	xx
	[exclusion criterion 2]	x	xx
	[exclusion criterion 3]	x	xx

^a More than one criterion may be marked per subject.^b Denominator for percentages is the total number of screen failures.

Table 10: Treatment Compliance by Study Day and Treatment Group, Safety Population

Summary	Nitazoxanide 500 mg (N=X)					Placebo (N=X)				
	Visit 2 Day 7	Visit 3 Day 14	Visit 4 Day 21	Visit 5 Day 28	Final Pill Count ^a	Visit 2 Day 7	Visit 3 Day 14	Visit 4 Day 21	Visit 5 Day 28	Final Pill Count ^a
Number of Subjects Completing Visit	X	X	X	X	X	X	X	X	X	X
Number of Subjects Compliant with Study Treatment	X	X	X	X	X	X	X	X	X	X
Mean Cumulative Number of Pills Taken	X.X	X.X	X.X	X.X	X.X	X.X	X.X	X.X	X.X	X.X
Mean Percentage of Pills Taken	X.X	X.X	X.X	X.X	X.X	X.X	X.X	X.X	X.X	X.X

N = Number of subjects in the Safety Population.

Note: To be considered compliant at a visit, subjects must have taken at least 75% of their expected pills. Compliance for final pill count requires subjects take at least 42 pills.

^a Final pill count will include Day 28 and Day 60 pill counts. Subjects with pill counts at both visits will use the Day 60 pill count as the final pill count.

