11.4.2 Analysis Populations

The safety population (grouped by actual treatment received) will include all subjects who are randomized, have received at least one dose of study treatment and have at least one safety assessment.

The modified intent-to-treat (mITT) population includes all randomized subjects who received at least one dose of assigned study drug. Analyses are performed according to randomized treatment assignment, not the treatment received.

The per-protocol (PP) population will include all subjects who met all inclusion/exclusion criteria, complied with the assigned study product, complied with the daily diary, and were followed up until resolution of symptoms, or completed 180 days without resolution of symptoms.

A subject is considered to be compliant with the assigned study product if he/she takes at least 75% of the scheduled doses through 28 days, and does not receive additional nitazoxanide before their primary outcome is observed.

A subject is considered to be compliant with the daily diary if he/she is missing no more than 1.5/7 days per week over the 8 weeks.

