3.3. Study Definitions and Derived Variables

Diarrhea:

Diarrhea will be defined as Type 6 or 7 on the Bristol Stool chart.

Baseline Value:

The baseline value will be defined as the last value obtained prior to the first dose of study product unless otherwise noted.

Additional Nitazoxanide:

Any nitazoxanide reported as a concomitant medication will be considered additional nitazoxanide.

Initial Clinical Resolution of Norovirus Symptoms:

Clinical resolution of Norovirus symptoms will be assessed from the daily diary by the subject and will be defined as:

- Cessation of vomiting and,
- No stools classified by the Bristol Stool Chart as diarrhea (Type 6 or 7).

Subjects will need to have at least two consecutive daily diary entries where they reported no vomiting, no Bristol Stool Type 6, and no Bristol Stool Type 7 to meet the criteria for initial clinical resolution. There are several variables in the daily diary that indicate whether the subject had diarrhea or vomiting for that day.

Daily Diary Diarrhea Questions:

- Phase 1 (Treatment Phase):
 - Number of Bristol Type 6 stools? (Quantitative)
 - Were there too many Bristol Type 6 stools to count? (Qualitative)
 - Number of Bristol Type 7 stools? (Quantitative)
 - Were there too many Bristol Type 7 stools to count? (Qualitative)
- Phase 2 (Longitudinal Phase):
 - Did you have diarrhea today? (By diarrhea, we mean at least ONE bowel movement that could be described as Type 6 or 7.) (Qualitative)

Daily Diary Vomiting Questions:

- Phase 1 (Treatment Phase):
 - Did you have to take another dose because you threw up the first dose within 1 hour? (Qualitative)
 - How many times did you vomit today? (Quantitative)
- Phase 2 (Longitudinal Phase):
 - Did you vomit today? (Qualitative)

For a day to count towards clinical resolution during the treatment phase, the following responses must be recorded in the daily diary entry:

- Both quantitative diarrhea questions must be 0

- Both qualitative diarrhea questions must be missing (i.e. not “yes”)
- The quantitative vomiting questions must be 0
- The qualitative vomiting question must be “no”

For a day to count towards clinical resolution during the longitudinal phase, the following responses must be recorded in the daily diary entry:

- The qualitative diarrhea question must be “no”
- The quantitative vomiting question must be 0

If a daily diary entry is missing, refer to the imputation rules in Section [6.5](#).

Viral Load:

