4.4.8. Treatment Compliance

Each subject will receive 2 bottles of nitazoxanide or placebo each containing 30 tablets, to be taken twice a day for 56 consecutive doses. If study subject has an episode of emesis or spits out the study medication within one hour of administration, the event will be documented in the subject's record and then the full dose will be re-administered one time only per scheduled dose. Subjects will be requested to bring study drug with them to all visits during the Treatment Phase. Remaining pill count will be done by the site staff during each visit to assess compliance. If subjects forget to bring in their study drug or they lose their container, subject interview and study diary will be used to confirm medication adherence.

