6.3.2. Per Protocol (PP) Population

The PP population will include all subjects who met all inclusion/exclusion criteria, complied with the assigned study product, complied with the daily diary, and were followed up until resolution of symptoms, or completed 180 days without resolution of symptoms.

A subject is considered to be compliant with the assigned study product if he/she takes at least 75% of the scheduled doses through 28 days and does not receive additional nitazoxanide (defined as in [Section 3.3](#)) before their primary outcome is observed. A subject is compliant with the daily diary if he/she is missing no more than 1.5/7 days per week over the first 8 weeks (Day 1 through Day 60).

This analysis set will be used for all efficacy analyses and will be considered secondary to analyses conducted in the mITT population.

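### SAP Table 10 counts drug compliance in tablets although the rule is in scheduled doses, so a subject with many missed doses and some re-doses can be counted compliant below 75%

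*SAP*

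**What the plan says.** The definition is in scheduled doses. Under Protocol Section 11.4.2 a subject complies if "he/she takes at least 75% of the scheduled doses through 28 days" and takes no additional nitazoxanide before the primary outcome. SAP Section 6.3.2 repeats this ("takes at least 75% of the scheduled doses through 28 days"), and the matching exclusion reason in Table 7 is "Received less than 75% of scheduled doses through 28 days". SAP Section 9.2 restates the rule and then points to Table 10 for the number of compliant subjects.

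The Table 10 footnote is in tablets: "To be considered compliant at a visit, subjects must have taken at least 75% of their expected pills", and at the end "Compliance for final pill count requires subjects take at least 42 pills".

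On supply and re-dosing, SAP Section 4.4.8 says "Each subject will receive 2 bottles of nitazoxanide or placebo each containing 30 tablets, to be taken twice a day for 56 consecutive doses". After emesis or spitting out within one hour, "then the full dose will be re-administered one time only per scheduled dose". The same section and Protocol Section 6.5 make the count of remaining pills the compliance measure, with interview and diary as back-up when the drug or container is not available. Protocol Section 7 tells subjects to skip a missed dose, so its tablet stays in the bottle.

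The treatment-phase diary asks "Did you have to take another dose because you threw up the first dose within 1 hour" (SAP Section 3.3). Listing 12 shows the answer as Yes/No by study day. Listing 8 sets diary-reported missed doses, by morning and evening, beside the final pill count. Neither item is linked to the compliance rule.

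**The concern.** Tablets gone and scheduled doses taken are the same number only when nobody re-doses. Each repeat removes a tablet without adding a scheduled dose, so the error can only run toward compliant. It is concentrated in subjects who vomit, and cessation of vomiting is part of the primary endpoint.

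At stake are the number of compliant subjects and the two pill means in Table 10. If the same count feeds Section 6.3.2, membership of the per-protocol set is also at stake, and the primary analysis is repeated in that set. Only 31 subjects were enrolled. With about 15 per arm if balanced, one misclassified subject is 1/15, or about 7% of an arm.

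**Working it through.** **Inputs.** 56 scheduled doses and 2 x 30 = 60 tablets (SAP 4.4.8); threshold 75% (SAP 6.3.2); cut of 42 pills (Table 10); at most one repeat per scheduled dose (SAP 4.4.8). Re-dose frequency is not given, so r below is assumed. That repeats come out of the counted kit is an inference: no separate replacement supply is described.

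**The plan's own figure.** 0.75 x 56 = 42. The pill cut is the scheduled-dose cut with tablets put in place of doses.

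**Floor under the pill rule.** Let s be scheduled doses taken and r re-doses, with r no larger than s. Tablets gone = s + r. Passing needs s + r of at least 42, so the smallest s that passes is 42 - r.

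| r (assumed) | smallest s that passes | s/56 | r/s |
|---|---|---|---|
| 0 | 42 | 75.0% | 0% |
| 1 | 41 | 73.2% | 2.4% |
| 2 | 40 | 71.4% | 5.0% |
| 4 | 38 | 67.9% | 10.5% |
| 8 | 34 | 60.7% | 23.5% |
| 14 | 28 | 50.0% | 50.0% |
| 21 | 21 | 37.5% | 100% |

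Each re-dose lowers the floor by 1/56 = 1.8 percentage points. The last row is an arithmetic limit, in which every dose taken is repeated.

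**Who can be wrongly passed.** A true failure has s of 41 or less, so at least 56 - 41 = 15 scheduled doses were missed. A subject who re-doses often but takes 42 or more scheduled doses is classified correctly.

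**How often.** This was simulated with 400,000 subjects per setting, doses independent, and assumed values for per-dose adherence and for the share of taken doses repeated:

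| adherence | repeated | wrongly passed | their mean s/56 |
|---|---|---|---|
| 80% | 5% | 8.0% | 72.3% |
| 70% | 10% | 39.5% | 70.3% |
| 70% | 20% | 62.0% | 68.7% |
| 90% or more | 2% to 20% | about 0 | not informative |

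Over all settings tried (adherence 65% to 95%), passing with 33 or fewer scheduled doses (33/56 = 59%) never exceeded 2% of subjects.

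**Pill means.** These are inflated without any missed dose. A subject who takes all 56 doses and re-doses 4 times uses 60 tablets. If 56 is the expected number, that is 60/56 = 107%.

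**The case against.** The strongest reply is that Table 10 is a descriptive Safety Population table, while Section 6.3.2 and Table 7 are worded in scheduled doses. The SAP nowhere says that the 42-pill cut decides per-protocol membership. This stands, and it limits the point. It does not remove it, because Section 9.2 ties Table 10 to the scheduled-dose definition and the SAP sets out no other derivation.

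A reader might infer that subjects who vomit generally pass with well under 75% of their doses, and that the per-protocol comparison is biased toward no effect. The documents do not support either step. A false pass needs 15 or more missed doses as well as re-doses. One to four re-doses lower the floor only to between 73% and 68%. Vomiting is not required for entry, whereas active diarrhea is (Protocol Section 5.1). Misclassification can occur in either arm, so dilution is possible but its direction and size are not derived.

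It is also tempting to argue that re-dosing exhausts the kit and so causes under-dosing. That is a different case. A subject at the 42-tablet cut still has 60 - 42 = 18 tablets. One who empties the kit after 8 re-doses has taken 52 of 56 scheduled doses (93%) and is compliant. SAP Section 4.4.5 does not name the source of replacement tablets, and inpatients are supplied under the site's own procedures.

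Finally, Listings 8 and 12 would let a careful reader find affected subjects among 31, and a pill count is a defensible main measure. Both are true, but the listings do not correct the counts and means in Table 10.

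**Conclusion.** The point holds as a mismatch of units. Table 10 reports compliance in tablets under a rule written in scheduled doses, with no correction for permitted re-doses. Subjects with at least 15 missed doses and some re-doses can be counted compliant at (42 - r)/56, which is 73%, 68% and 61% for r = 1, 4 and 8. Mean pills taken and mean percentage taken are inflated as measures of dosing.

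The size rests on assumed re-dose counts and on repeats coming from the counted kit. At adherence of 90% or more the number wrongly passed is about zero. Any effect on the per-protocol set is conditional on the pill count being used to derive it. In that case some under-dosed subjects may be retained and may dilute a secondary analysis. The mITT primary analysis is unaffected. This is a minor point, worth correcting because it is cheap.

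**What to change.** Define one variable, scheduled doses taken, with a cut of 42 of 56, and use it in SAP Sections 6.3.2 and 9.2, Tables 7 and 10 and Listing 8. Derive it as tablets gone minus diary-recorded re-doses. Cross-check it against 56 minus diary-recorded missed doses, which Listing 8 already carries, and say in advance which source prevails when they disagree. Report re-doses as a separate row in Table 10. State in Section 6.3.2 that this variable decides product compliance for the per-protocol set.

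The cost is SAP wording and one derived variable; no new data are needed. The subtraction may not be exact. The re-dose item is one Yes/No per diary day under twice-daily dosing, so two repeats in a day count as one. It asks about vomiting, whereas the re-dosing rule also covers doses spat out. Missing diary days carry no information, and SAP Section 14.1.3 already concedes unresolved timing problems in the diary. The cross-check is therefore needed.

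Separately, the passages on re-dosing (Protocol Section 7, SAP Sections 4.4.5 and 4.4.8) and on the 60-tablet supply (Protocol Section 5.3.1, SAP Section 4.4.3) should be reconciled, so that it is clear where repeat tablets come from and whether the pill count includes them. No dosing rule is proposed here.

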14.1.2 Demographic Data by Study Group

Table 11: Summary of Categorical Demographic and Baseline Characteristics by Treatment Group

Variable	Characteristic	Nitazoxanide 500 mg (N=X)		Placebo (N=X)		All Subjects (N=X)	
		n	%	n	%	n	%
Sex	Male	x	xx	x	xx	x	xx
	Female						
Ethnicity	Not Hispanic or Latino	x	xx	x	xx	x	xx
	Hispanic or Latino						
	Not Reported						
	Unknown						
Race	American Indian or Alaska Native	x	xx	x	xx	x	xx
	Asian						
	Native Hawaiian or Other Pacific Islander						
	Black or African American						
	White						
	Multi-Racial						
	Unknown						
Duration of Symptoms	Acute (less than 14 days)	x	xx	x	xx	x	xx
	Chronic (14 days or greater)						
Transplant Type	Solid organ	x	xx	x	xx	x	xx
	Hematopoietic Stem Cell Transplant						
Age Range	Pediatric (12-17 years)	x	xx	x	xx	x	xx
	Adult (\geq 18 years)						

N = Number of subjects enrolled.

Tables with similar format:

Table 12: Summary of Categorical Demographic and Baseline Characteristics by Site

[Implementation Note: Treatment Groups will be replaced with Site Names.]

Table 13: Summary of Continuous Demographic and Baseline Characteristics by Treatment Group

Variable	Statistic	Nitazoxanide 500 mg (N=X)	Placebo (N=X)	All Subjects (N=X)
Age	Mean	xx	xx	xx
	Standard Deviation	xx	xx	xx
	Median	xx	xx	xx
	Minimum	x	x	x
	Maximum	x	x	x

N = Number of subjects enrolled.

Tables with similar format:

Table 14: Summary of Continuous Demographic and Baseline Characteristics by Site

[Implementation Note: Treatment Groups will be replaced with Site Names.]

